this table may be found in Appendix 10.						Da	ıy 1							
Hours Relative to Dosing at 0 hour	-1.0	-0.5	0	0.5	1	2	3	4	6	8	10	12	Day 1 activities at time = 0 hour are prior to the dose, except for study intervention administration.	
Blinded study intervention administration			X										Participants should fast for at least 10 hours prior to dosing, except for periods in which food effects are investigated. See Section 5.3.2 and Section 6.1.1 for additional information.	
Standardized meals/snack								X			X		See Section 5.3.2.	
Respiratory rate and oral body temperature			X				X			X			See Section 8.3.2.2 and Section 8.3.2.3 for additional details.	
Supine BP and pulse rate			X	X	X	X	X	X	X	X	X		Triplicate measurements at all times. See Section 8.3.2.1 for additional details. In the optional cohort of Japanese participants, vital sign assessments may be performed at selected time-points to be decided based on emerging data from previous cohort(s).	
12-Lead ECG	X	X	X	Х	X	X	Х	X	X	X	X		Triplicate measurements at all timepoints. See Section 8.3.3 for additional details. In the optional cohort of Japanese participants, ECG assessment may be performed at selected time-points to be decided based on emerging data from previous cohort(s).	
Continuous cardiac telemetry			X	\rightarrow	→	→	\rightarrow	→	\rightarrow	X			Telemetry monitoring will not be performed in the optional cohort of Japanese participants. See Section 8.3.3.1 for additional details.	
Blood sampling for:														
PF-06954522 plasma PK			X	X	X	X	X	X	X	X	X	X	See Section 8.5 for additional details.	
CCI														
Retained Research Samples for Biomarkers [Prep B2.5]			X		X								To be collected as outlined in Section 8.7.2.	

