5.3.2. Meals and Dietary Restrictions

- Participants must abstain from all food and drink (except water) for at least 8 hours prior to all safety laboratory evaluations.
- Participants must abstain from all food and drink (except water) for at least 10 hours prior to the collection of the predose PK sample.
- Water is permitted until 1 hour prior to study intervention administration. Water may be consumed without restriction beginning 1 hour after dosing. Noncaffeinated drinks (except grapefruit or grapefruit-related citrus fruit juices (see below) may be consumed with meals and the evening snack.

Dosing under fasted conditions (Day 1 only):

• The standard morning breakfast will not be offered on Day 1. Participants will remain fasted for 4 hours following dosing.

Dosing under fed conditions (Day 1 only):

- A morning meal will be served to participants approximately 30 minutes prior to dosing and is expected to be completed approximately 10 minutes prior to dosing. Participants will be encouraged to consume the entire meal.
 - For planned assessment of food effect, this morning meal will be a high-fat (approximately 50% of total caloric content of the meal) and high-calorie (approximately 800-1000 calories) breakfast. The breakfast will consist of approximately 150 protein calories, 250 carbohydrate calories, and 500-600 fat calories. An example test meal would be: 2 eggs fried in butter, 2 strips of bacon (or 50 g of meat or sausage), 2 slices of toast with butter, 4 ounces (approximately 112 grams) of hash brown potatoes, and 8 fluid ounces (240 mL) of whole milk.
 - A standard breakfast may be provided during other study periods/cohorts, if deemed necessary to meet study objectives (see Section 4.1). If this is the case, details will be provided to the investigator in writing.
- While inpatient, the meals consumed are expected to follow the restrictions outlined below:
 - No food will be allowed for at least 4 hours post-dose.
 - Lunch will be provided approximately 4 hours after dosing.
 - Dinner will be provided approximately 9 to 10 hours after dosing.

- Participants may delay or skip postdose meals or be offered an alternative meal in case of nausea or vomiting. In such cases, the proportion of each meal consumed by the participants will be recorded.
- An evening snack may be permitted.

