6.1.1. Administration

For fasted periods:

 Following an overnight fast of at least 10 hours, participants will receive study intervention at approximately 0800 hours (plus or minus 2 hours) without breakfast on Day 1.

For fed period(s):

Following an overnight fast of at least 10 hours, participants will receive breakfast approximately 30 minutes prior to dosing on Day 1 which is to be completed within approximately 20 minutes as outlined in Section 5.3.2. The participants will then receive study intervention approximately 10 minutes after completion of the meal at approximately 0800 hours (plus or minus 2 hours).

On Day 1 of each period, investigator site personnel will administer a single oral dose of study intervention with ambient temperature water to a total volume of approximately 240 mL. Study intervention will be administered according to the EDR.

In order to standardize the conditions on PK sampling days, all participants will be required to refrain from lying down (except when required for BP, pulse rate, and ECG measurements), eating, and drinking beverages other than water during the first 4 hours after dosing.

Administration of study intervention(s) at the site will be performed by an appropriately qualified and trained member of the study staff as allowed by local, state, and institutional guidance.

Following administration of study intervention(s) at the site, participants will be observed for up to 2 hours post-dose by an appropriately qualified and trained member of the study staff. Appropriate medication and other supportive measures for management of a medical emergency will be available in accordance with local guidelines and institutional guidelines.

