8.3.3. Electrocardiograms

Standard 12-lead ECGs will be collected at times specified in the SoA section of this protocol using an ECG system that automatically calculates the HR and measures PR, QT, QTcF, and QRS intervals. All scheduled ECGs should be performed after the participant has rested quietly for at least 5 minutes in a supine position.

Triplicate 12-lead ECGs will be obtained approximately 2 to 4 minutes apart; the average of the triplicate ECG measurements collected at -1.0, -0.5, and 0 hours pre-dose on Day 1 of each period will serve as each participant's baseline QTcF value.

To ensure safety of the participants, a qualified individual at the investigator site will make comparisons to baseline measurements. Additional ECG monitoring will occur if a) the mean value from the triplicate measurements for any postdose QTcF interval is increased by ≥60 ms from the baseline and is >450 ms; or b) an absolute QT value is ≥500 ms for any scheduled ECG. If either of these conditions occurs, then a single ECG measurement must be repeated at least hourly until QTcF values from 2 successive ECGs fall below the threshold value that triggered the repeat measurement.

For single ECG collection, additional ECG monitoring will occur if a) a postdose QTcF interval is increased by ≥60 ms from the baseline **and** is >450 ms; or b) an absolute QT value is ≥500 ms for any scheduled ECG. If either of these conditions occurs, then 2 additional ECGs will be collected approximately 2 to 4 minutes apart to confirm the original measurement. If the QTcF values from these repeated ECGs remain above the threshold value, then a single ECG must be repeated at least hourly until QTc values from 2 successive ECGs fall below the threshold value that triggered the repeat measurement.

If a) a postdose QTcF interval remains ≥ 60 ms from the baseline and is ≥ 450 ms; or b) an absolute QT value is ≥ 500 ms for any scheduled ECG for greater than 4 hours (or sooner, at the discretion of the investigator); or c) QTcF value get progressively longer, the participant should undergo continuous ECG monitoring. A cardiologist should be consulted if QTcF values do not return to less than the criteria listed above after 8 hours of monitoring (or sooner, at the discretion of the investigator).

In some cases, it may be appropriate to repeat abnormal ECGs to rule out improper lead placement as contributing to the ECG abnormality. It is important that leads be placed in the

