9.3.1.1. Electrocardiogram Analyses

Changes from baseline for the ECG parameters HR, QT interval, QTcF, PR interval, and QRS complex will be summarized by treatment and time. The frequency of uncorrected QT values above 500 ms will be tabulated.

The number (%) of participants with maximum post-dose QTcF values and maximum increases from baseline in the following categories will be tabulated by treatment:

Safety QTcF Assessment

egree of Prolongation Mild (ms) Moderate (ms) Severe (ms)	Moderate (ms) Severe (ms)	Mild (ms)	Degree of Prolongation
---	---------------------------	-----------	------------------------

Absolute value	>450-480	>480-500	>500
Increase from baseline		30-60	>60

If more than 1 ECG is collected at a nominal time after dose administration (for example, triplicate ECGs), the mean of the replicate measurements will be used to represent a single observation at that time point. If any of the 3 individual ECG tracings has a QTcF value >500 ms, but the mean of the triplicates is not >500 ms, the data from the participant's individual tracing will be described in a safety section of the CSR in order to place the >500 ms value in appropriate clinical context. However, values from individual tracings within triplicate measurements that are >500 ms will not be included in the categorical analysis unless the average from the triplicate measurements is also >500 ms. Changes from baseline will be defined as the change between the postdose QTcF value and the average of the pre-dose triplicate values at -1, -0.5, and 0 hours pre-dose on Day 1.

In addition, an attempt will be made to explore and characterize the relationship between plasma concentration and QT interval length using a PK/PD modeling approach. If a PK/PD relationship is found, the impact of participant factors (covariates) on the relationship will be examined. The results of such analyses may not be included in the CSR.

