#### 3.1.3. Vital Signs

Single supine blood pressure and pulse rate measurements will be taken at screening, follow-up visit and at early termination (if applicable). Triplicate supine measurements will be taken at all other times as detailed in the Schedule of Activities (SoA) in the protocol. The average of the triplicate measurements will be calculated prior to analyzing the data. Respiratory rate and temperature will be measured at each timepoint specified in the protocol.

Baseline for these measures will be defined as the average of the triplicates (if applicable) at last nominal pre-dose measurement time in each study period.

The following endpoints will be determined:

- Change from baseline (CFB) in systolic and diastolic BP, pulse rate, respiratory rate and temperature.
- The minimum and maximum post-dose systolic and diastolic BP, pulse rate, respiratory rate and temperature.

The maximum increase and decrease from baseline over all measurements taken postdose for systolic and diastolic BP, pulse rate, respiratory rate and temperature values

The maximum increase from baseline will be calculated by selecting the maximum change from baseline over the respective period, except in the case where a participant does not show an increase. In such an instance, the minimum decrease should be taken. Similarly, the maximum decrease from baseline will be determined by selecting the minimum value of the change from baseline. In cases where a participant does not show a decrease, the minimum increase should be taken.

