## 3.1.5. Electrocardiograms

A single 12-lead ECG will be obtained on all participants at screening, follow-up visit and at early termination (if applicable). 12-lead ECGs will be recorded in triplicate at all other times as detailed in the SoA in the protocol. The average of the triplicate readings collected at each assessment time will be calculated for each ECG parameter. If one or two of the triplicates are missing, the non-missing values will be used for the average, and missing values will not be imputed.

If any of the 3 individual ECG tracings has a QTcF value >500 msec, but the mean of the triplicates is not >500 msec, the data from the participant's individual tracing will be described in a safety section of the CSR in order to place the >500- msec value in appropriate clinical context. However, values from individual tracings within triplicate measurements that are >500 msec will not be included in the categorical analysis unless the average from the triplicate measurements is also >500 msec.

The average of the triplicate ECG measurements over the 3 pre-dose measurement times (-1H, -0.5H, and pre-dose 0H; total of 9 ECG measurements) collected before morning dose administration on Day 1 will serve as each participant's baseline value in each study period.

ECG endpoints include heart rate, QT interval, PR interval and QTcF and QRS complex. If not supplied QTcF will be derived using Fridericia's heart rate correction formula [1]:

QTcF (msec) = QT (msec) / (RR)1/3 where RR (sec) = 60/HR (if RR not provided).

The following endpoints will be determined:

• Change from baseline in QT, QTcF, PR, QRS interval and heart rate

- The maximum post-dose QTcF, heart rate, PR and QRS interval
- The maximum increase from baseline over all measurements taken post-dose for QTcF, heart rate, PR and QRS values

The maximum increase from baseline will be calculated by selecting the maximum change from baseline over the respective period, except in the case where a participant does not show an increase. In such an instance, the minimum decrease should be taken.

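### Does a fed period need its own rule on whether baseline ECGs and vital signs come before or after breakfast?

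*SAP*

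**What the plan says.** - **ECG baseline.** SAP 3.1.5 defines it, for each period, as follows: "The average of the triplicate ECG measurements over the 3 pre-dose measurement times (-1H, -0.5H, and pre-dose 0H; total of 9 ECG measurements". Protocol 8.3.3 agrees ("the average of the triplicate ECG measurements collected at -1.0, -0.5, and 0 hours pre-dose on Day 1 of each period"), and so does Protocol 9.3.1.1 ("the average of the pre-dose triplicate values at -1, -0.5, and 0 hours pre-dose on Day 1"). None of the three mentions a meal.
- **Vital-sign baseline.** SAP 3.1.3 uses the "average of the triplicates (if applicable) at last nominal pre-dose measurement time in each study period". In Protocol Table 2 (Section 1.3), blood pressure, pulse, respiratory rate and temperature have a single pre-dose time, 0 h.
- **Meaning of 0 h.** A Table 2 note reads: "Day 1 activities at time = 0 hour are prior to the dose, except for study intervention administration".
- **Fed breakfast.** Under Protocol 6.1.1, fed participants "receive breakfast approximately 30 minutes prior to dosing on Day 1 which is to be completed within approximately 20 minutes". The dose follows about 10 minutes after the meal ends. Protocol 5.3.2 gives the same times.
- **Fasting.** Table 2 says: "Participants should fast for at least 10 hours prior to dosing, except for periods in which food effects are investigated". Separately, Protocol 5.3.2 bars food "for at least 10 hours prior to the collection of the predose PK sample", with no exception for fed periods.
- **Order and temperature.** Protocol 8.1 and 8.3.2.1 place ECG, blood pressure and pulse ahead of a nearby blood draw. Protocol 8.3.2.3 requires 15 minutes without eating before an oral temperature.
- **Reporting.** SAP 5.2 reports each dietary allocation separately and keeps fed-period placebo out of the pooled placebo group. SAP 6 counts dietary allocation as part of treatment.

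**The concern.** Read at nominal times, the 0 h set in a fed period falls after breakfast. Read through the fasting, order and temperature rules, it falls before. The SAP selects baseline by nominal time, so either practice enters the analysis under the same 0 h label.

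Change from baseline in ECG and vital signs belongs to the primary safety endpoint. Fed changes could therefore rest on a different reference state from fasted changes while appearing in the same family of tables and plots. The measures involved are ones the protocol watches: heart rate and PR interval (Protocol 2.3.1), and temperature and blood pressure (Protocol 4.2). Protocol 4.2 also makes fed safety and tolerability a stated purpose of the food assessment. Finally, the individual QTcF change criterion in Protocol 7.1.3 depends on a baseline.

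**Working it through.** **1. The plan's own figures.** Three pre-dose times × 3 replicates = 9 ECG tracings, as SAP 3.1.5 states. The meal runs from −30 to −10 min, which is 20 min, as in Protocol 6.1.1. The gap from meal end to dose is 10 min.

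**2. State of the baseline under each reading.**

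| Baseline | 0 h set just before dose | 0 h set before breakfast |
|---|---|---|
| ECG (9 tracings) | 3 pre-meal, 3 at meal start, 3 post-meal | 0 of 9 post-meal |
| BP and pulse (3 readings) | 3 of 3 post-meal | 0 of 3 post-meal |
| Respiratory rate, temperature (1 reading) | 1 of 1 post-meal | 0 of 1 post-meal |

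The baseline is arithmetically defined either way. What is left open is whether the participant has eaten.

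**3. Which rules conflict with a post-meal 0 h set?**
- Predose PK sample: a 10 h fast cannot hold 10 min after a meal. Direct conflict.
- Oral temperature: 15 − 10 = 5 min short. Direct conflict.
- ECG, BP and pulse: no fasting rule of their own. They move ahead of the meal only because they precede the PK draw.

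The Table 2 fed exemption concerns the fast before *dosing*. It is compatible with a predose PK sample drawn before breakfast, after the overnight fast that Protocol 6.1.1 requires in fed periods too.

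**4. Would a post-meal ECG and BP set fit in 10 min?** A triplicate at 2 to 4 min spacing spans 2 × (2 to 4) = 4 to 8 min.
- End to end after one 5 min rest: 5 + (4 to 8) + (4 to 8) = 13 to 21 min, which is 3 to 11 min too long.
- Interleaved: 5 + (4 to 8) = 9 to 13 min, which fits at the shortest spacing.

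No section requires end-to-end recording, so timing alone does not rule out a post-meal ECG and BP set.

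**5. Would a pre-meal set fit?** Between −60 and −30 min there are 30 min.
- End to end: 3 × (4 to 8) + (4 to 8) = 16 to 32 min, or 21 to 37 min with one rest.
- BP interleaved with one ECG triplicate: 5 + 3 × (4 to 8) = 17 to 29 min.

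Temperature and the PK draw come on top. It is feasible but tight. The 0 h set crowds the −0.5 h set, and at the long end recording would have to start before −1 h.

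**6. Size, under an assumption.** The documents give no meal effect. Suppose a meal shifts pulse by *d*. The two readings then differ by *d* in the vital-sign pulse baseline and by 3*d*/9 = *d*/3 in the ECG heart-rate baseline (counting only the 0 h set as post-meal). For *d* = 2, 5 or 10 bpm, the ECG figure is 0.7, 1.7 or 3.3 bpm.

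**7. Outputs touched.** Five vital-sign and three ECG mean-change plots (5 + 3 = 8), with their summary tables, for about 8 active and 2 placebo participants. The mixed model in SAP 6.3.2 uses AUC and Cmax only.

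**The case for a change.** The strongest opposing case is that the pre-meal answer emerges only by combining scattered rules, while the schedule and both baseline definitions, taken literally, give another. Three further points support it.

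- **Thin control.** With fed placebo not pooled, about 2 fed placebo participants remain, so interpretation leans on change from baseline. This stands in part. Those 2 share the meal and the baseline rule, so a meal shift acts on both groups alike, but the comparison is imprecise.
- **Shared displays.** The QTcF-versus-concentration scatter in SAP 6.1.5 states no fed exclusion, and mean-change plots carry one line per treatment. However, treatment includes dietary allocation, so fed data have their own symbol or line, and SAP 5.2 has dietary allocations reported separately.
- **Attribution.** From Period 2 onward, a pre-dose Day 1 value meeting a categorical criterion is credited to the previous period's treatment (SAP 6.1.3 and 6.1.5). A post-meal 0 h reading in a fed Period 5 could thus be charged to Period 4. This stands as a possibility under the post-meal reading. For vital signs, every value meeting the criteria is listed, so it would be visible.

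The link to the QTcF criterion in Protocol 7.1.3 is weak where the fed period is Cohort 1's last, as anticipated, because no later dose remains in that cohort. It would matter more if the fed period came earlier, which Protocol 4.1 permits. No view is taken here on that criterion.

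**Conclusion.** No change follows. The sections do pull in different directions, but the gap is one that site staff and analysts can fill from rules already in the protocol. Because 0 h means only before the dose, a set taken before breakfast is consistent with the PK fast, the assessment order and the temperature rule.

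The state can often be checked afterwards. Dose times and predose PK sample times are both recorded (Protocol 6.5 and 8.5). ECG and blood pressure precede that draw, so a sample taken more than 30 minutes before the dose places them before the meal. Protocol 8.5 also allows timing changes to be documented without an amendment.

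Fixing the choice in the SAP would be a trade-off and not a clear gain. A pre-meal baseline gives fed changes that include the meal effect, so they still could not be set directly against fasted changes, and it compresses three spaced ECG sets. A baseline immediately before dosing absorbs some of the meal effect but conflicts with the temperature rule and the PK fast. Neither choice restores comparability. Absolute values are summarised in any case, and fed placebo participants share whichever baseline is used.

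The size is small: at most 3 of 9 ECG tracings clearly post-meal, and one vital-sign set, in an optional period whose safety analysis is descriptive and untested. This rests on two assumptions: that the site follows one practice for all participants within a fed period, and that blinded staff do not vary timing by treatment. No size or direction of meal effect is claimed.

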2.3.1. Risk Assessment

Potential Risk of Clinical Significance	Summary of Data/Rationale for Risk	Mitigation Strategy						
Study Intervention(s) PF-06954522								
Gastrointestinal adverse reactions	The potential risks are based on product labeling for injectable GLP-1R agonists (ie, liraglutide, exenatide, semaglutide and dulaglutide).	Study includes inpatient monitoring of the participants following administration of a single dose of the study intervention. Participants are monitored to prevent potential sequelae of any severe gastrointestinal reactions, eg, dehydration.						
Hypoglycemia	Clinical trials with injectable GLP-1R agonists have not demonstrated an increased risk for hypoglycemia. However, when administered in combination with anti-diabetic agents that are known to have an increased risk of hypoglycemia (such as insulin or sulfonylureas), an increased risk for hypoglycemia was observed.	The participants enrolled will not have diabetes and will not be receiving anti-diabetic agents. Study includes inpatient monitoring of the participants following administration of a single dose of the study intervention.						
Increased heart rate and decreased PR interval	Based on the product labeling for the injectable GLP-1R agonist liraglutide for obesity, mean increases in resting heart rate ranged 2 to 3 bpm in clinical trials, with some participants experiencing greater increases in resting heart rate, up to 10-20 bpm. Increased heart rate and decreased PR interval was observed in a single-dose NHP study of PF-06954522.	Study includes inpatient monitoring of the participants through periodic vital sign assessment, ECGs and telemetry following administration of a single dose of the study intervention.						
Other potential risks associated with long-term dosing of marketed GLP-1R agonists include thyroid C-cell tumors, pancreatitis, impairment in renal function, diabetic retinopathy complications, suicidal ideation/behavior and acute gallbladder disease.	These potential risks are based on product labeling for injectable GLP-1R agonists (ie, liraglutide, dulaglutide, exenatide and semaglutide).	This is a single dose study in healthy participants. Participants with a personal or family history of MTC or MEN2; with acute pancreatitis or a history of chronic pancreatitis are not eligible for study entry. Study includes inpatient monitoring and safety laboratory surveillance (eg, calcitonin, amylase, lipase, eGFR) of the						

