# 6.1.3. Vital Signs

Absolute values and changes from baseline (as defined in Section 3.1.3) in supine systolic and diastolic blood pressure, respiratory rate, temperature, and pulse rate will be listed, and summarized by treatment and timepoint, according to sponsor reporting standards using the safety population defined in Section 4.

Mean absolute values and mean changes from baseline for systolic and diastolic blood pressure, respiratory rate, temperature, and pulse rate will be plotted against time point. On each plot, there will be 1 line for each treatment with all doses on the same plot. Corresponding individual plots of changes from baseline will also be produced for each treatment.

Maximum and minimum absolute values and changes from baseline (as defined in Section 3.1) for supine vital signs will also be summarized descriptively by treatment using categories as defined in Appendix 2.

Numbers and percentages of participants meeting the categorical criteria will be provided. All planned and unplanned post dose time points will be counted in these categorical summaries. All values meeting the criteria of potential clinical concern will be listed.

Values meeting the categorical criteria occurring pre-dose on Day 1 for each period starting with Period 2, will be attributed to the dose from the previous period (e.g., for cohort 1, an occurrence pre-dose at Period 2 Day 1 will be attributed to the Period 1 dose). For any participant who starts the study after Period 1, the same considerations as described in Section 6.1.2 apply.

Data collected at screening that are used for inclusion/exclusion criteria, will be considered source data, and will not be required to be reported, unless otherwise noted. Unplanned assessment will be listed but will be excluded from safety summary except for categorical summaries.

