# 6.1.5. Electrocardiograms

Absolute values and changes from baseline in QT, heart rate, QTcF, PR and QRS will be summarized by treatment and timepoint using sponsor reporting standards, using the safety analysis set defined in Section 4. Baseline is as defined in Section 3.1.5.

Mean changes from baseline in QT, heart rate and QTcF will be plotted against time post-dose. On each plot there will be one line for each treatment. Corresponding individual plots of changes from baseline will also be produced for each treatment.

Changes from baseline in QTcF will also be plotted separately against drug concentrations of PF-06954522. This will be a scatter plot for all observations where QTcF and drug concentration are recorded. Placebo data will also be included (with drug concentration set to zero). Different symbols will be used for each treatment.

Maximum increase from baseline for QTcF, heart rate, PR and QRS values will be summarized by treatment according to sponsor reporting standards.

ECG endpoints and changes from baseline (QTcF [1], PR and QRS) will also be summarized descriptively by treatment (if applicable) using categories as defined in Appendix 2. Numbers and percentages of participants meeting the categorical criteria will be provided. All planned and unplanned postdose time points will be counted in these categorical summaries.

Values meeting the categorical criteria occurring pre-dose on Day 1 for each period starting with Period 2, will be attributed to the treatment from the previous period (e.g., for cohort 1, an occurrence pre-dose at Period 2 Day 1 will be attributed to the Period 1 dose). For any participant who starts the study after Period 1, the same considerations as described in Section 6.1.2 apply.

Listings of participants with any single post-dose value >500msec will also be produced for QTcF.

Data collected at screening that are used for inclusion/exclusion criteria, will be considered source data, and will not be required to be reported, unless otherwise noted. Unplanned assessment will be listed but will be excluded from safety summary except for categorical summaries.

In addition, an attempt will be made to explore and characterize the relationship between plasma concentration and QT interval length using a PK/PD modeling approach. If a PK/PD relationship is found, the impact of participant factors (covariates) on the relationship will be examined. The results of such analyses may not be included in the CSR.

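### The protocol names PR shortening as a potential risk, but the SAP's per-participant PR extremes and categories run only upward and its change plots omit PR, so the planned by-timepoint table is not backed by any participant-level view of shortening

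*SAP*

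**What the plan says.** The risk table in Protocol 2.3.1 pairs a rise in heart rate with a fall in PR. It gives the source for this compound as "Increased heart rate and decreased PR interval was observed in a single-dose NHP study of PF-06954522". The stated mitigation is inpatient monitoring by vital signs, ECG and telemetry.

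SAP 3.1.5 defines two per-participant PR endpoints. One is the highest post-dose value; the other is "The maximum increase from baseline over all measurements taken post-dose for QTcF, heart rate, PR and QRS values". A participant with no increase is represented by the smallest decrease. SAP 6.1.5 carries this forward: "Maximum increase from baseline for QTcF, heart rate, PR and QRS values will be summarized by treatment according to sponsor reporting standards". Both PR categories in SAP Appendix 2 are upward: a maximum of 300 msec or more, and a rise of 50% or more from a baseline of 200 msec or less.

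For plots, SAP 6.1.5 says "Mean changes from baseline in QT, heart rate and QTcF will be plotted against time post-dose", with matching individual plots. PR is not among them.

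PR does appear in the by-timepoint table: "changes from baseline in QT, heart rate, QTcF, PR and QRS will be summarized by treatment and timepoint using sponsor reporting standards". SAP 5.2.1 gives the statistics as n, mean, SD, median, minimum and maximum. This meets Protocol 9.3.1.1, which asks for PR change by treatment and time.

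Unplanned ECGs are handled separately: "Unplanned assessment will be listed but will be excluded from safety summary except for categorical summaries". Within the categorical tables, "All planned and unplanned postdose time points will be counted in these categorical summaries".

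Vital signs are treated in both directions. SAP 3.1.3 defines minimum values and maximum decreases as well as maxima and increases. SAP 6.1.3 says that these variables, including "respiratory rate, temperature, and pulse rate will be listed, and summarized by treatment and timepoint", are both listed and summarised. The corresponding ECG sentence in 6.1.5 says only that values are summarised.

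**The concern.** Safety is the primary objective and about 8 participants receive each dose in Cohort 1. A basic question in a first-in-human study is whether an observed effect is one person repeatedly or several people. For PR lengthening the SAP answers with participant-level extremes and counts. For PR shortening, the direction the protocol names, it gives only rows by timepoint. The heart-rate half of the same risk is served better: it has a maximum, a maximum increase, and mean and individual change plots.

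Two things are missing from the specified outputs. The first is a participant-level display of PR decrease to set beside pooled placebo. The second is any summary that would register shortening at an unplanned ECG, since those values enter only the categorical tables and the PR categories look upward.

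**Working it through.** **Inputs from the documents.** There are 8 active participants per Cohort 1 period (Protocol 9.5). There are 12 scheduled post-dose triplicate ECG times: 0.5, 1, 2, 3, 4, 6, 8, 10, 24, 36, 48 and 72 h (Protocol Tables 1 and 2). Baseline is the mean of three triplicate means (SAP 3.1.5). The placebo comparison uses 8 profiles: 2 per period × 4 fasted periods of Cohort 1, assuming Period 5 is the fed period.

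**Assumptions.** The documents give no PR variability. I take an SD of 6 ms per triplicate mean (range 4 to 8) and independent errors. The 30 ms drop and the 25 ms count below are illustrative, not proposed thresholds. The plan states no figure of its own to reproduce. Simulated results use 40,000 groups of 8.

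**1. What the planned table already shows.** The SD of a change at one time is 6 × √(1 + 1/3) = 6.9 ms. The SE of an 8-against-8 difference in means is 6.9 × √(2/8) = 3.5 ms.
- A 10 ms drop in everyone at 6 times therefore separates from placebo by 10/3.5 = 2.9 SE at any one of those times. A maximum-decrease summary gives 3.2 SE. At SD 4 the pair is 4.3 and 5.1; at SD 8 it is 2.2 and 2.2.
- If one of 8 drops 30 ms at 2 times, the lowest by-timepoint minimum averages -33 ms (-17 with no effect). The smallest per-participant minimum is the same number by identity.

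**2. Participants who shorten together.** If k of 8 drop 30 ms at the same 4 times, the expected mean at those times is -30k/8:

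| k | mean (ms) | median (ms) |
|---|---|---|
| 1 | -3.75 | -1.2 |
| 2 | -7.5 | -2.9 |
| 4 | -15 | -15 |
| 8 | -30 | -30 |

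The mean over those 4 times has SD 6 × √((1/4 + 1/3)/8) = 1.6 ms. One affected participant against four is then plainly visible in the planned table.

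**3. Participants who shorten at different times.** Compare (i) one participant dropping 30 ms at 4 times with (ii) four participants each dropping 30 ms at a different one of those times. Each timepoint has one affected value of 8 in both cases, so each row has the same distribution: mean -30/8 = -3.8 ms, minimum about -30 ms.

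| | No effect | (i) | (ii) |
|---|---|---|---|
| Median maximum increase (planned), ms | about +9.7 | +9.5 | +9.6 |
| Median maximum decrease (not planned), ms | -9.7 | -10.5 | -18.9 |
| Participants with a fall of 25 ms or more | 0.01 | 1.0 | 3.1 |

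At SD 4 the median maximum decreases are -7.0 and -17.6 ms and the counts 1.0 and 3.4. At SD 8 they are -14.0 and -20.4 ms, and 1.2 and 3.0, with about 0.3 of 8 reaching 25 ms under no effect.

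**4. An exact example without a model.** Take changes of -30, -5, -2, 0, 0, 2, 3 and 4 ms at every time. Give them to the same participants throughout, or rotate them among the 8. The by-timepoint tables are identical, yet 1 of 8 or 8 of 8 participants reach -20 ms at some time. In the rotated set the planned maximum increase is +4 ms for everyone. In the fixed set it would expose the one participant, because that participant is at -30 ms at every reading.

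**The case against.** The best counter-argument is that step 3 is a constructed case. After a single oral dose an effect would be expected to cluster in time, and step 2 shows that the planned mean and median then track the number affected. A negative median alone means that at least half shortened at that time. This stands. A reader might infer that the table says nothing about how many participants shortened, and that goes too far.

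A reader might also infer that the SAP departs from the protocol or conceals shortening. The documents support neither. Protocol 9.3.1.1 asks for PR change by treatment and time, and the SAP delivers it. The PR criterion in Protocol Appendix 8 is itself prolongation. The risk row promises monitoring and no particular analysis.

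Other safeguards count participants or look at individuals. Protocol 6.6.1 has a stopping criterion at 50% of active participants with similar clinically significant ECG abnormalities, in either direction. Section 6.4.3 allows unblinded participant-level review, 8.3.3 has site staff compare ECGs with baseline, and 7.1.3 sends clinically relevant findings to the AE tables. These protect conduct, but none supplies an end-of-study display of PR decrease.

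The sponsor reporting standards cited in 6.1.5 are not in the documents and may add listings or tables. The missing mention of a listing in 6.1.5 may be a variation in wording and not a decision. Both limit how firmly an absence can be asserted.

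Finally, a summarised maximum decrease does not itself count participants. That is correct; of the changes proposed, only individual plots or a downward category do so.

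**Conclusion.** The point holds as a minor reporting improvement. For the PR direction named in the protocol, the specified outputs contain no per-participant extreme, category or profile, and no summary that takes in unplanned ECGs. The by-timepoint table reveals shortening and, when it clusters in time, gives a fair idea of how many participants are involved. In general it cannot separate repeated shortening in one participant from shortening in several at different times.

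The size of the gap depends on assumed variability and on staggered timing. Where participants shorten at the same times, little is lost. SAP 5.1 applies no test or decision rule, so no conclusion of the trial turns on this. The underlying PR finding is nonclinical.

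**What to change.** In SAP 3.1.5 and 6.1.5, add minimum post-dose PR and maximum decrease from baseline in PR. Use the rule already written in SAP 3.1.3 and summarise by treatment beside the pooled placebo group of SAP 5.2. Add PR to the mean and individual change-from-baseline plots in 6.1.5; the individual plots are what will show how many participants shortened.

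Optionally, add a PR-decrease category to Appendix 2 with a cut-off chosen by the sponsor. Under the present rule on unplanned assessments, this is the only change that would count shortening at unplanned ECGs.

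The cost is SAP wording, a few table rows and one set of plots, from data already collected. The drawback is a little more output and one trap in reading it. A maximum decrease over 12 times averages about -10 ms with no drug effect (assumed SD 6 ms; -6.5 to -13 ms for SD 4 to 8), so it must be read against placebo.
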